### **Definition of Rx Days (Days Relative to the Date of First Dose of Study Drug)**

Rx Days are calculated for each time point relative to the date of first dose of study drug. They are defined as the number of days between the day of the first dose of study drug and the specific time point. Rx Days are negative values when the time point of interest is prior to the first study drug dose day. Rx Days are positive values when the time point of interest is on or after the first study drug dose day. The day of the first dose of study drug is defined as Rx Day 1, while the day prior to the first study drug dose is defined as Rx Day –1 (there is no Rx Day 0).

### **Definition of Analysis Windows**

All time points and corresponding time windows are defined based on Rx Days.

Analysis windows are constructed using the following algorithm:

- Determine the nominal Rx day for each visit (e.g., Week 4 [4 weeks after Baseline visit] equals Rx Day 29).

- In order to include all post baseline data, the first post-baseline interval starts on the first day after the first dose of study drug (Rx Day 2).
- Determine the window around a specific nominal Rx day by adding or subtracting half of the interval between adjacent visits (e.g., days between Week 4 and Week 8 is 28). The threshold between adjacent visits is determined by splitting the interval evenly between the visits. If the resulting split is between Rx days, then the threshold is determined as the midpoint between the adjacent visits. If the resulting split is on an Rx day, then the threshold is determined as being between that Rx day and the Rx day prior to it (e.g., the split between Week 4 and Week 8 would be between Rx Days 43 and 44).
- If more than one assessment is included in a time window the assessment closest to the nominal day will be used. If there are two observations equidistant to the nominal day, the later one will be used in analyses. If more than one assessment is included on the same day, then the worst assessment on that day will be used in analyses, except those specified in Section 11.0.

For subjects who were randomized and not dosed, the date of randomization will be used for determining window definitions.

The following analysis windows have been specified:

**Table 1. Visit Windows for Analysis of Vital Signs, PASI, BSA Involvement, sPGA, Urinalysis, Targeted Safety Laboratory Testing (ITT/Safety Populations)**

Window Label	Target Day	Interval
Baseline	1	≤ 1
Week 4	29	[2, 43]
Week 8	57	[44, 71]
Week 12	85	[72, 99]
Week 16	113	[100, 127]
Week 20	141	[128, 155]
Week 24	169	[156, 183 a ]

Rx Day calculated relative to first dose date of study drug. For subjects randomized but not dosed, Rx Day calculated relative to Randomization.

Targeted Safety Laboratory Testing includes CBC with differential count (hematology), ALT, AST, gamma-GT, alkaline phosphatase (AP) and serum creatinine.

a. For safety analyses (urinalysis and targeted laboratory testing): The minimum of upper bound and 105 or 7 days after the last dose for risankizumab and FUMADERM®, respectively.

**Table 2. Visit Windows for Analysis of DLQI, PPASI, PSSI, NAPPA-CLIN, PSS, SF-36, PBI, HADS, PtGA, EQ-5D-5L (ITT Population)**

Window Label	Target Day	Interval
Baseline	1	≤ 1
Week 16	113	[2, 141]
Week 24	169	[142, 197]

Rx Day calculated relative to first dose date of study drug. For subjects randomized but not dosed, Rx Day calculated relative to Randomization.

**Table 3. Visit Windows for Analysis of Complete Safety Laboratory Testing (Safety Population)**

Window Label	Target Day	Interval
Baseline	1	$\leq 1$
Week 8	57	[2, 85]
Week 16	113	[86, 141]
Week 24	169	[142, 197 a ]

Rx Day calculated relative to first dose date of study drug. For subjects randomized but not dosed, Rx Day calculated relative to Randomization.

Complete Safety Laboratory Testing includes all laboratory parameters (see [Table 8](#)) excluding CBC with differential count (hematology), ALT, AST, gamma-GT, alkaline phosphatase (AP) and serum creatinine.

a. For safety analyses: The minimum of upper bound and 105 or 7 days after the last dose for risankizumab and FUMADERM®, respectively.

**Table 4. Visit Windows for Analysis of ECG (Safety Population)**

Window Label	Target Day	Interval
Baseline	1	$\leq 1$
Week 24	169	[2, 337 a ]

Rx Day calculated relative to first dose date of study drug. For subjects randomized but not dosed, Rx Day calculated relative to Randomization.

a. The minimum of upper bound and 105 or 7 days after the last dose for risankizumab and FUMADERM®, respectively.

**Table 5. Visit Windows for Summary of Study Drug Injection of Risankizumab**

Window Label	Target Day	Interval
Baseline	1	$\leq 1$
Week 4	29	[2, 43]
Week 16	113	[44, 155]

Rx Day calculated relative to the first dose date of study drug.

No global imputation is taking place at the database level. Efficacy related imputations are outlined in [Section 10.1.2](#). There is no imputation for missing values in the safety analyses.

## **Rounding of Numeric Results**

Rounding will be performed for presentation of results. No rounding will be performed before or during analyses. The ROUND function of SAS will be used to round results.

When dichotomizing continuous variables from single observations, associated continuous variables will be rounded to 9 decimal points before applying the cutoff point to determine the response status (for example, percent change from baseline in PASI score will be rounded to 9 decimal places before comparing to 90%).

The mean, median and quartiles will be rounded for presentation to 1 decimal more than the data entered into the database. The standard deviation will be rounded to 2 decimal places more than the data entered into the database. The minimum and maximum values will be presented as entered into the database.

Probabilities will be rounded to 3 decimal places before assignment of statistical significance and will be presented in rounded format. Probabilities that round to zero or are reported by SAS as zero will be presented as "< 0.001." Probabilities that round to 1 or are reported by SAS as 1 will be presented as "> 0.999."

## **7.0 Demographics, Baseline Characteristics, Medical History, and Previous/Concomitant Medications**

### **7.1 Demographic and Baseline Characteristics**

Demographic and baseline characteristics will be summarized for each arm and overall for the ITT population. The number of observations, mean, standard deviation, median, first and third quartile, minimum and maximum will be summarized for continuous variables; and treatment groups will be compared using a one-way analysis of variance (ANOVA) model with treatment as the independent factor. Categorical or discrete variables will be summarized via counts and percentages; and treatment groups will be compared using a two-sided Pearson's Chi-Square test (or Fisher's exact test if expected cell count < 5).

The following demographic and baseline parameters will be summarized.

### **Subject Demographics**

- Sex (male, female)
- Age (years), defined as the number of years from date of birth to date of first drug
- Age categories (< 40 years,  $\geq$  40 – < 65 years,  $\geq$  65 years)
- Race (White, Black or African American, Asian, American Indian or Alaska Native, Native Hawaiian or Other Pacific Islander, Multi Race)
- Asian race (Japanese, Chinese, Korean, Taiwanese, Other)
- Ethnicity (Hispanic or Latino, Not Hispanic or Latino)
- Body weight (kg)
- Body weight category ( $\leq$  100 kg, > 100 kg)
- Height (cm)
- BMI (kg/cm^2)
- BMI category (< 25,  $\geq$  25 – < 30,  $\geq$  30)

### **General Baseline Characteristics**

- PASI (Psoriasis Area and Severity Index)
- BSA (Body Surface Area)
- sPGA categories (Static Physician Global Assessment)
- NAPPA-CLIN (Nail Assessment in Psoriasis and Psoriatic Arthritis)
- PSSI (Psoriasis Scalp Severity Index)
- PPASI (Palmoplantar Psoriasis Area Severity Index)
- PSS (Psoriasis Symptom Severity)
- SF-36 (Short Form 36)
- PBI (Patient Benefit Index)
- HADS (Hospital Anxiety & Depression Scale)
- Patient Global Assessment (PtGA)

- EQ-5D-5L (European Quality of Life – 5 Dimensions 5 Level)
- Dermatology Life Quality Index (DLQI)
- CASPAR:
  - Total score
  - Evidence of current personal psoriasis (yes, no)
  - Evidence of history of psoriasis
    - personal history of psoriasis (yes, no)
    - Evidence of family history of psoriasis (yes, no)
  - Psoriatic nail dystrophy (yes, no)
  - Negative test for presence of rheumatoid factor (yes, no)
  - Current or history of dactylitis (yes, no)
  - Radiographic evidence of juxtaarticular bone formation (yes, no)

### **Disease History**

- Time since initial diagnosis of Plaque Psoriasis (years)
- Time since initial symptoms of Plaque Psoriasis (years)
- Prior phototherapy (yes, no)
- For subjects with prior phototherapy: Type of prior phototherapy (UVA, UVB Broad Band, UVB Narrow Band, Balneotherapy, Other) including outcome (success, failure)

### **General Use**

- Smoking history (Never-smoked, Former-smoker, Currently smokes)
- Alcohol History (Non-drinker, Former-drinker, Currently drinks)

Physical Exam and Pregnancy Test will be presented in listing format in the full data listings.

### **TB History/PPD Test/TB Prophylaxis**

- Former BCG vaccination (yes, no)

- Induration of Tuberculin PPD skin test (mm)
- PPD test (positive, negative) – *the PPD test is considered positive for an induration of 5 mm or greater*
- QuantiFERON-TB Gold or equivalent test (positive, negative, indeterminate)
- TB test (positive, negative, indeterminate) – *in the event that both a PPD test and QuantiFERON-TB gold or equivalent test are performed, the result of the QuantiFERON-TB gold or equivalent test will supersede the result of the PPD test*
- Active TB (yes, no)
- Latent TB (yes, no)

## 7.2 Medical History

Medical history will be summarized using body systems and condition/diagnosis as captured on the eCRF. The body systems will be presented in alphabetical order and the conditions/diagnoses will be presented in alphabetical order within each body system. The number and percentage of subjects with a particular condition/diagnosis will be summarized for each treatment arm. Subjects reporting more than one condition/diagnosis within a body system will be counted only once for that body system.

## 7.3 Previous Treatment and Concomitant Medications

Prior and concomitant medications will be summarized by generic name, separately for Psoriasis Therapy and other medications, per the category documented on the eCRF. A prior medication is defined as any medication taken prior to the first dose of study drug. A concomitant medication is defined as any medication that started prior to the first dose of study drug and continued to be taken after the first dose of study drug or any medication that started after the first dose of study drug, but not after the last dose of study drug. The number and percentage of subjects who had taken medications will be summarized by generic drug name assigned by the World Health Organization (WHO) for both prior and concomitant medications.

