**Diagnosis and Main Criteria for Inclusion/Exclusion (Continued):****Main Exclusion (Continued):**

- Severe gastro-intestinal disease, such as a known active gastro-duodenal ulcer,
- Inability to understand the complexity of FUMADERM® dosing regimen,
- Any other exclusionary condition provided in Fumaderm® local label,
- Any of the following risk factors for renal toxicity:
  - peripheral vascular disease
  - diabetes mellitus with microalbuminuria (UACR > 30 mg/g), at Screening Visit,
  - systolic blood pressure measurement of > 140 mmHg or a diastolic blood pressure measurement of > 90 mmHg at the Screening visit, unless there is confirmation from an internist or a cardiologist that no renal or cardiovascular risk is associated with the elevated blood pressure.
  - history of congestive heart failure (NYHA Class III or IV\*)

**Investigational Product:** Risankizumab**Doses:** 150 mg at Weeks 0 and 4, and 16.**Mode of Administration:** Subcutaneous Injection (SC) (pre-filled syringe)**Investigational Product:** FUMADERM® INITIAL and FUMADERM® provided as study medication**Doses:** QD to TID**Mode of Administration:** Oral**Duration of Treatment:** The treatment duration will be 16 weeks for risankizumab and 24 weeks for FUMADERM®.**Criteria for Evaluation:****Efficacy:**

The primary efficacy endpoint is the proportion of subjects with a  $\geq 90\%$  improvement in Psoriasis Area and Severity Index (PASI90) at Week 24.

Secondary efficacy variables are:

PASI, Body Surface Area (BSA), static Physician Global Assessment (sPGA), Palmoplantar psoriasis Severity Index (PPASI), Psoriasis Scalp Severity Index (PSSI), Nail Assessment in Psoriasis and Psoriatic Arthritis (NAPPA-CLIN), Total Score Psoriasis Symptom Scale (PSS), Dermatology Life Quality Index (DLQI), Short Form 36 (SF-36) Physical Component Summary (PCS) and Mental Component Summary (MCS) Scores, Patient Benefit Index (PBI), Hospital Anxiety and Depression Scale (HADS) Patient Global Assessment (PtGA), European quality of life – 5 dimensions 5 Level (EQ-5D-5L)

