## **5.0 Investigational Plan**

### **5.1 Overall Study Design and Plan: Description**

This is a randomized, controlled, multicenter, open-label study with blinded assessment of efficacy to demonstrate the efficacy and safety of SC risankizumab in adult subjects with moderate to severe plaque psoriasis who are naïve to and candidates for systemic therapy as compared with oral FUMADERM® provided as study medication. Eligible male and female subjects with moderate to severe plaque psoriasis will be selected to participate in the study according to the selection criteria.

The study will include a 30-day screening period and a 24 week active-controlled treatment period followed by a follow-up phone call at Week 31 for subjects that do not elect to enroll into the extension study. The maximum study duration is approximately 35 weeks for subjects that do not elect to enroll into the extension study and approximately 28 weeks for subjects that do participate in the extension study. This study was designed to enroll 110 subjects to meet scientific and regulatory objectives without enrolling an undue number of subjects in alignment with ethical considerations. Therefore, if the target number of subjects has been enrolled, there is a possibility that additional subjects in screening will not be enrolled.

After meeting the selection criteria, enrolled subjects will be randomly assigned in a 1:1 ratio to one of two arms as shown below:

- Risankizumab 150 mg SC at Week 0/Day 1, Week 4 and Week 16 or,
- Oral FUMADERM® INITIAL provided as study medication starting at Week 0/Day 1 until Week 2 and FUMADERM® provided as study medication starting at Week 3 until Week 24 (last intake in the morning on the day of Week 24 visit):

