**5.5.2.2****Identity of FUMADERM® INITIAL and FUMADERM® Investigational Product**

The two formulations of Fumaderm are used in this study are FUMADERM® INITIAL and FUMADERM® gastro-resistant tablets, FUMADERM® INITIAL being the low dose formulation to be taken in the first weeks of treatment before moving to FUMADERM®.

**Table 5. FUMADERM® INITIAL and FUMADERM® Pre-Specified Dosing Schedule (in the Absence of an Adjustment to the Efficacy and/or Safety Response):**

Week	Dosage (n of Tablets/Day)		
	Morning	Noon	Evening
FUMADERM® INITIAL			
0	-	-	1
1	1	-	1
2	1	1	1
FUMADERM®			
3	-	-	1
4	1	-	1
5	1	1	1
6	1	1	2
7	2	1	2
8 – 24*	2	2	2

\* Last intake of FUMADERM® in the morning on the day of Week 24 visit.

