#### **4.2                   Design Diagram**

This is a randomized, controlled, multicenter, open-label study with blinded assessment of efficacy to demonstrate the efficacy and safety of SC risankizumab in adult subjects with moderate to severe plaque psoriasis who are naïve to and candidates for systemic therapy as compared with oral FUMADERM® provided as study medication. Eligible male and female subjects with moderate to severe plaque psoriasis will be selected to participate in the study according to the selection criteria. Approximately 110 subjects will be enrolled in this study.

[figure not shown]
The study will include a 30-day screening period and a 24 week active-controlled treatment period followed by a follow-up phone call at Week 31 for subjects that do not elect to enroll into the extension Study M15-997.

After meeting the selection criteria, enrolled subjects will be randomly assigned in a 1:1 ratio to one of two arms as shown below:

- Risankizumab 150 mg SC at Week 0/Day 1, Week 4 and Week 16 or,
- Oral FUMADERM® INITIAL provided as study medication starting at Week 0/Day 1 until Week 2 and FUMADERM® provided as study medication starting at Week 3 until Week 24 (last intake in the morning on the day of Week 24 visit)

A schematic of the study design is shown below in [Figure 1](#).

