**Figure 1. Study Design Schematic**

**4.3 Sample Size**

Using a two-sided Chi squared test at level of significance 5%, the sample size of 110 (2 × 55) subjects will provide 94% power assuming response rates of the primary endpoint (PASI 90 at Week 24) of 70% for risankizumab and 35% for FUMADERM®.

These assumptions are in line with what has been observed in recent studies for risankizumab (63/83 (75.9%) at Week 24) and FUMADERM® 61/273 (22.3%) of the subjects achieved PASI 90 at Week 16 in the FUMADERM® arm in the BRIDGE trial.

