### **Risankizumab Exposure (in Days)**

Risankizumab Exposure (days) = Date of last injection – Date of first injection + 84 days.

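### The SAP 7.3 cut-off for newly started concomitant medication falls at Week 16 on risankizumab but Week 24 on FUMADERM, so the descriptive medication tables compare unequal periods

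*SAP*

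**What the plan says.** SAP 7.3 has two routes to being concomitant. A medication begun before first dose qualifies if it continues afterwards. A medication begun on study qualifies if it is "any medication that started after the first dose of study drug, but not after the last dose of study drug". The section applies this to two summaries by generic name, one for psoriasis therapy and one for other medications, each giving numbers and percentages of subjects.

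The dosing schedules in SAP 4.2 are "Risankizumab 150 mg SC at Week 0/Day 1, Week 4 and Week 16" for one arm and, for FUMADERM, daily tablets with "last intake in the morning on the day of Week 24 visit". The Protocol synopsis puts it as "The treatment duration will be 16 weeks for risankizumab and 24 weeks for FUMADERM". The primary endpoint is PASI 90 at Week 24 in both arms.

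Elsewhere the SAP looks further past the last injection. The risankizumab exposure formula in Section 9.0 takes the date of the last injection and ends "Date of first injection + 84 days". Section 11.2.1 counts TEAEs for 105 days after the last risankizumab dose and 7 days after the last FUMADERM dose. Nothing in SAP 7.3, or in the SAP's summary of changes, extends the last dose in this way for medication.

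**The concern.** A last-dose cut-off works for a daily tablet, because last dose and end of treatment nearly coincide. It works less well when the other arm is injected at Weeks 0, 4 and 16 and assessed at Week 24. The same rule then closes the two columns of one table at different times.

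The period lost on risankizumab leads up to the primary assessment. Treatment is open-label with only the efficacy assessor blinded, and the imputation rules in SAP 10.1.3 contain no step that makes a subject a non-responder for taking other psoriasis therapy. A reader who asks whether co-treatment differed between arms will turn to these tables and may not notice that they cover different lengths of time. At stake is a fair descriptive comparison of co-medication, not the efficacy test.

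**Working it through.** **Inputs**
- Cut-off for new starts: last dose of study drug (SAP 7.3).
- Last scheduled dose: Week 16 on risankizumab, Week 24 on FUMADERM (SAP 4.2; Protocol 5.5.2.2, Table 5 footnote: "Last intake of FUMADERM® in the morning on the day of Week 24 visit").
- Day convention: Week w is Rx Day 7w + 1 (SAP 6.0). Week 16 = Day 113, Week 24 = Day 169, Week 31 = Day 218.
- Visit window: plus or minus 4 days (Protocol 5.1).

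**Reproducing the plan's own figure.** Protocol 5.1 places the Week 31 call about 15 weeks after the last risankizumab dose and 7 weeks after the last FUMADERM dose.
- 218 − 113 = 105 days = 15 weeks
- 218 − 169 = 49 days = 7 weeks

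Both agree, which confirms last doses 8 weeks apart.

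**Counting window for new starts, subjects dosed as scheduled**
- Risankizumab: 113 − 1 = 112 days
- FUMADERM: 169 − 1 = 168 days
- Gap: 169 − 113 = 56 days = 8 weeks, and 56/168 = 33% of the treatment period
- Gap with visit windows: (169 − 4) − (113 + 4) = 48 days to (169 + 4) − (113 − 4) = 64 days

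**Illustration.** Assume the same constant rate of first new starts in both arms. If a true proportion q starts a new medication by Week 24, the proportion counted on risankizumab is 1 − (1 − q)^(112/168).

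| True q (shown for FUMADERM completers) | Shown on risankizumab | Subjects of 55, FUMADERM vs risankizumab |
|---|---|---|
| 20% | 1 − 0.8^(2/3) = 13.8% | 11.0 vs 7.6 |
| 40% | 1 − 0.6^(2/3) = 28.9% | 22.0 vs 15.9 |
| 60% | 1 − 0.4^(2/3) = 45.7% | 33.0 vs 25.1 |

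The values of q are hypothetical; the documents give no start rates. The table concerns new starts only. If a fraction c of subjects is already counted through medication continued from before first dose, and new starts are independent of that, the shortfall in the displayed total shrinks by the factor 1 − c.

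**Early stoppers.** The rule also drops later starts for anyone who stops drug early but stays on study, in either arm. For a risankizumab subject last injected at Week 4 (Day 29), the uncounted stretch to Week 24 is 169 − 29 = 140 days.

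**The case against.** The strongest reply is that little depends on these tables.

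- **No efficacy analysis uses the definition.** The CMH analysis, non-responder imputation, LOCF and multiple imputation are all specified without it. A reader might infer that the primary result is biased; the documents do not support that. This part of the objection stands in full.
- **Prohibited psoriasis therapy is counted elsewhere.** Protocol Table 1 keeps its restrictions in force through 15 weeks after the last risankizumab dose, which covers Weeks 16 to 24. SAP 7.4 reports the number and percentage of subjects who received prohibited treatment and states no last-dose limit. It would therefore be wrong to infer that rescue with a prohibited therapy goes unseen. But SAP 7.4 gives a category count and not the drug. It does not capture permitted medication such as the low-potency topical corticosteroids allowed by footnote c of Table 1. This part stands only in part.
- **The differing windows are not a contradiction.** The exposure (+84 days), TEAE (+105 days) and medication windows are separate definitions for separate purposes, and the SAP never says that they share an end. They are simply not aligned. The mismatch is still awkward: a drug started for a risankizumab TEAE at Week 20 would not be concomitant although the event is counted.
- **The loss is not exclusive to risankizumab.** A FUMADERM subject who stops early also loses later starts, and the Protocol introduction cites 24% discontinuation for adverse events on FUMADERM in a previous trial. The clean contrast of 112 against 168 days belongs to subjects dosed as scheduled.

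**Conclusion.** The concern holds, within limits. Followed as written, SAP 7.3 gives concomitant-medication tables that cover new starts for 112 days on risankizumab and 168 days on FUMADERM in subjects dosed as scheduled. They omit Days 114 to 169 from the risankizumab column only for such subjects. This follows from the text and day arithmetic and needs no assumption.

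The percentages in the illustration do rest on assumptions: equal constant start rates, hypothetical values of q, and new starts only. Risankizumab can therefore appear to need less co-medication than it did, but a reader should not conclude that it will, or by a known amount. Medication started by Week 16, or continued from before first dose, is counted in both arms.

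The consequence is an unequal descriptive comparison. The primary estimate, alpha and power are unchanged. It is worth correcting before database lock because the uncounted weeks are those just before the primary assessment and the correction is easy.

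**What to change.** In SAP 7.3, define a concomitant medication in both arms as one taken on or after the first dose of study drug and started no later than the Week 24/ET visit, whatever the date of last dose. Use this definition for both the Psoriasis Therapy table and the other-medication table. The planned window becomes 168 days in each arm.

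Borrowing the exposure window, last injection plus 84 days, would not be enough. For a risankizumab subject still on study whose last injection was at Week 4, it ends on Day 29 + 84 = Day 113 and leaves Days 114 to 169 uncounted.

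The cost is one sentence and a matching line in the SAP's summary of changes. No new data are needed, since Protocol 5.2.3.2 already requires every medication received during the study to be recorded with start and end dates. Risankizumab counts may rise, as may counts for any subject who stopped drug early but stayed on study.
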